### Diary Data

For the analysis involving diaries, time-points will be defined as non-overlapping periods. See [Appendix B](#) for definition of time intervals. Missing daily micturition data will be estimated as the following:

1. If one out of three days is missing, the mean of the remaining days will be used to impute the micturition data for the missing day/days.
2. The LOCF/BOCF imputations will be carried out for time-intervals with missing diary data. For intervals where less than two days of diary data are available, the previous available 3-day post-baseline interval values will then be carried forward.

Micturition volume is collected on one day only therefore if it is missing at a visit the previous visit's data will be carried forward.

Note: In subjects who withdraw after a minimum of 2 weeks of treatment, attempts should be made to perform a urodynamic assessment, provided that they have not missed any doses in the three days previous to the visit.

### **Plasma concentrations**

#### **Concentrations below the limit of quantification**

In listings BLQ values will be reported as "<LLQ", where LLQ will be replaced with the value for the lower limit of quantification.

#### **Missing concentrations values**

In summary tables, statistics will be calculated having set concentrations to missing if the following case is true:

- A concentration has been collected as ND (ie not done) or NS (ie no sample).

Note that summary statistics will not be presented at a particular time point if more than 50% of the data are missing.

### **Date of Birth**

In the case where the whole Date of Birth is not entered, the last day of the month will be used to impute the missing day, and 31st December will be used if both the day and month are missing.

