#### 4.1. Inclusion Criteria

Subject eligibility should be reviewed and documented by an appropriately qualified member of the investigator's study team before subjects are included in the study.

Subjects must meet all of the following inclusion criteria to be eligible for enrollment into the study:

1. Male or female subjects aged 6-17 years 11 months (age at time of first dose); that is subjects who have passed their sixth birthday but not reached their eighteenth birthday.
2. Subjects with stable neurological disease and clinically- or urodynamically-demonstrated NDO, confirmed urodynamically at Visit 2, by detrusor overactivity or decreased bladder compliance, with decreased maximum cystometric bladder capacity.

NOTE: Subjects with hypocontractile bladder, detrusor underactivity, or a 'flaccid' bladder should not be included.

3. Evidence of a personally signed and dated informed consent document indicating that the subject (or a legal representative) has been informed of all pertinent aspects of the study. In addition, an assent from the subject will be obtained when appropriate, and when the potential subject is capable of providing assent.
4. Female subjects who are of child-bearing potential (defined as  $\geq 9$  years old or have experienced menarche, whichever is earlier) must not be intending to become pregnant, currently pregnant, or lactating. The following conditions apply:
  - a. Subjects of childbearing potential must have a confirmed negative pregnancy test prior to randomization.
  - b. Subjects of child-bearing potential must agree to use effective contraception during the period of the trial and for at least 28 days after completion of treatment. Effective contraception includes abstinence.
  - c. Sexually active male subjects must agree to use effective contraception during the period of the trial and for at least 28 days after completion of treatment.

Further details of the definition of child-bearing potential and effective contraception may be found in Section 4.4.

5. Swallowing:
  - a. Subjects  $>25$  kg must already have the ability to swallow tablets whole, without chewing or crushing. The first dose of medication will be given in clinic under observation, and any subject not able to swallow tablets will be excluded from the study.

- b. Subjects  $\leq 25$  kg can either swallow the capsules whole or sprinkle on food.

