### 5.2. Per Protocol Analysis Set

*The Per Protocol Analysis Set will include all subjects who have completed the active comparator/efficacy phase of the study, and who have not violated any of the inclusion/exclusion criteria or deviated from the protocol in a way that could affect the efficacy outcome of the study.*

The PPAS for each cohort will be defined prior to unblinding.

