### **6.3. Pharmacokinetic Evaluations**

*Variation in the CYP2D6 gene plays a role in metabolism of active metabolite (5-HMT) of fesoterodine. The alleles which will be genotyped are \*3, \*4, \*5, \*6, \*7, \*8, \*10, \*14, \*17, \*18, \*21, \*36, \*41 and duplication. Homozygous or heterozygous combinations of \*3, \*4, \*5, \*6, \*7, \*8, \*14, \*17, \*18, and \*21 will be classified as poor metabolizer (PM) of CYP2D6. Other genotypes will be classified as extensive metabolizer (EM). CYP2D6 genotype and metabolizer status of subjects randomized to fesoterodine treatment will be reported as an individual-subject listing.*

For those subjects who are randomized to fesoterodine and who do not have sufficient laboratory documentation, a 2-ml whole blood sample will be collected for CYP2D6 genotype analysis. All samples will be discarded following analysis. Subjects who have prior laboratory documentation of their CYP2D6 genotype will not be required to submit a blood sample for pharmacogenomics. Subjects randomized to treatment with oxybutynin will also not be required to provide a sample for pharmacogenomic assessment.

Population pharmacokinetic analyses will be conducted via nonlinear mixed-effects modeling with the NONMEM® software, Version VI (ICON Development Solutions, [name]). Model-based parameter estimates for absorption rate constant (Ka), apparent oral clearance (CL/F) and volumes of distribution (Vd) will be determined to predict the area under the curve (AUC), maximum concentration (Cmax), time to reach Cmax (Tmax) and half-life of 5-HMT in patients randomized to fesoterodine treatment. Possible influences of patient covariates (eg, age, body weight, gender, CYP2D6 metabolizer status etc.) on 5-HMT exposure will be assessed.

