### **6.4. Covariates**

The baseline observation for the endpoint being analyzed will be used as a continuous covariate in any ANCOVA analyses.

Baseline weight will be used as a continuous endpoint in any ANCOVA analyses.

The following subgroups will be assessed for the primary endpoint:

Age: Ages  $\geq 6-9$ ,  $\geq 10-12$ ,  $\geq 13-17$

Weight: Cohort 1:  $\leq 50$  kg,  $>50$  kg, Cohort 2:  $\leq 20$  kg,  $>20$  kg

Gender: Male, Female

Region: Cohort 1: North America, Europe, Asia, Cohort 2: North America and Europe, Asia

Type of Underlying Disease: Congenital, Acquired, Unknown

Race: White, Asian, Black, Other (where Other includes: American Indian or Alaska Native, Native Hawaiian or other Pacific Islander)

Ethnicity: Hispanic/Latino, Not Hispanic/Latino

Underlying disease will be categorised as 'congenital' or 'acquired' and will be determined through manual review of medical history listings (by the clinician) for Cohort 1. If this is unable to be determined, this will be categorized as 'Unknown'. For Cohort 2 the answer to the question "Underlying Cause of Primary Diagnosis" on the Primary Diagnosis eCRF page will be utilized, for which the responses are 'Congenital' or 'Acquired'.

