Data from the active comparator phase of the study may be summarized, analyzed and reported after all subjects have either completed or withdrawn prior to the Week 12 visit or from both phases after all subjects in Cohort 1 have either completed or withdrawn prior to the end of the study (ie, prior to formal completion of the whole study for both cohorts). If performed, the results of these analyses will be assessed by the EDMC and will be available to limited members of the study team as a management tool in order to aid decision making, and may also be shared with regulators in order to facilitate timely discussion of the overall program; they will not be used to stop or modify the design of the study.

Descriptive subgroup analyses of the change from baseline to Week 12 in the primary endpoint will be produced by age group, weight group, race, ethnicity, gender, region and underlying type of disease.

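### SAP section 7 imputes partial birth dates to the latest possible date, so derived age is biased low and can come out as 5 for an eligible 6-year-old

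*SAP*

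**What the plan says.** SAP section 7, under Date of Birth, covers two cases. With month and year known, "the last day of the month will be used to impute the missing day". With only the year known, "31st December will be used if both the day and month are missing". No reason is given, and no clause keeps the result inside the eligible age range. The SAP's table of changes shows that the rule was added in version 1.1.

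Protocol section 4.1, criterion 1, admits "subjects who have passed their sixth birthday but not reached their eighteenth birthday", with age taken at first dose. SAP section 6.4 lists age among the factors under "The following subgroups will be assessed for the primary endpoint", in bands 6-9, 10-12 and 13-17. SAP section 8.2.1 says how they are used: "Descriptive subgroup analyses of the change from baseline to Week 12 in the primary endpoint will be produced by age group", along with other factors. Section 8.2.2 does the same for Cohort 2. SAP section 6.3 names age as a possible covariate for 5-HMT exposure.

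**The concern.** An imputed date should be right on average and should not produce a value that the trial already knows to be false. This rule fails on both counts. Taking the latest possible date pushes every error in the same direction, towards a younger child. And because enrolment requires the sixth birthday to have passed, a derived age of 5 in an enrolled child is almost always an artefact of the rule. Such a child has no row in the age-subgroup table and would look ineligible in the demographic summary.

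At stake is the accuracy of descriptive age data. Cohort 2 plans about 25 evaluable subjects per arm over three age bands, so even a few misplaced children would be visible there.

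**Working it through.** The documents give no figure for this point, so there is none to reproduce.

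**Inputs from the documents.** The two imputation rules (SAP 7); eligible age 6 to <18 years at first dose (Protocol 4.1); band cut-points 6, 10 and 13 (SAP 6.4).

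**Assumptions not in the documents.** Births and first doses are spread evenly over the year. For the band calculation, true ages are spread evenly over the 12 years from 6 to <18.

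**Step 1: average error.** A child born at fraction *u* of the year is treated as born at its end, so age is understated by 1 − *u* years, with mean 1/2. Enumerating calendar dates gives 0.4985 year: 99.7% too low, none too high, the rest born on 31 December. When only the day is missing, the mean is 0.0403 year × 365.25 = 14.7 days: 96.7% too low, none too high.

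**Step 2: true 6-year-olds derived as 5.** With 31 December as birthday, completed age is dose year − birth year − 1. A true 6-year-old whose birthday has already passed that year was born in dose year − 6 and becomes 5. If the first dose falls at fraction *v* of the year, the share affected is *v*.

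- Even timing: mean *v* = 1/2. Enumeration of 133,284 date pairs gives 49.8%.
- By quarter of first dose: 12%, 37%, 62% and 86% (quarter midpoints 0.125, 0.375, 0.625 and 0.875).
- Month known: 4.0%.

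**Step 3: leaving the correct age band.** The share crossing a cut-point is the mean shift across it in years, divided by 12.

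- 31 December, unbounded: ages only move down, across 6, 10 or 13. 3 × 0.5/12 = 12.5%.
- Month-end, unbounded: 3 × 0.0403/12 = 1.0%.
- 31 December, bounded to 6 to <18: only 10 and 13 remain. 2 × 0.5/12 = 8.3%.
- 1 July, unbounded: the error runs evenly from −0.5 to +0.5 year, so the mean shift is 0.125 in each direction. Cut-points 10 and 13 are crossed both ways, 2 × 0.25/12 = 4.17%. The limits at 6 and 18 are each crossed one way, 2 × 0.125/12 = 2.08%. Total 6.25%.
- 1 July, bounded: 4.17%.

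| Year-only rule | Leave correct band (enumerated) | Mean error in age |
|---|---|---|
| 31 December, as in SAP | 12.5% | −0.50 year |
| 31 December, bounded | 8.3% | −0.48 year |
| 1 July, unbounded | 6.2% | about 0 |
| 1 July, bounded | 4.15% | about 0 |

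Without a bound, 1 July still derives 12.4% of true 6-year-olds as 5 and about 12.5% of true 17-year-olds as 18. With the month known, the 15th leaves 0.95% of true 6-year-olds below 6, against 4.0% for month-end.

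**Step 4: where age enters.** The Cohort 1 ANCOVA has treatment, baseline and baseline weight (SAP 8.2.1). The Cohort 2 model has treatment and baseline (SAP 8.2.2). Cohort 1 is stratified by weight and Cohort 2 is not stratified (Protocol 5.3). Age is in none of these. It remains in demographics, the descriptive age subgroups, safety data read against age-appropriate norms (SAP 6.2) and, if the population PK analysis takes the imputed date, the covariate assessment.

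**The case against.** The strongest reply is that this is a contingency rule with no inferential consequence. Age is in no ANCOVA, the subgroup summaries are descriptive, population PK has its own plan, and the documents do not say that any birth date is incomplete. All of that stands, and it sets the size of the point.

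Four stronger readings are tempting and are not supported.

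- A reader might infer that eligible children would be counted as violators and lost from the per-protocol set, since SAP 5.2 keeps only subjects "who have not violated any of the inclusion/exclusion criteria". But eligibility is reviewed and documented by the site before inclusion (Protocol 4.1) and checked at Visits 1 and 2 (6.1, 6.2). SAP 5.2.1 leaves violations of major criteria to a sponsor determination before database lock. Nothing ties either to the imputed date.
- A reader might infer that the rule hides enrolled 18-year-olds by showing them as 17. That presupposes a subject whom the site check should already have excluded.
- A reader might infer that Cohort 2 is hit hardest because light children cluster near age 6. The documents give no age distribution.
- The version 1.1 log entry might be taken to show that partial dates occur. It shows only that a rule was written.

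It can also be said that the age bound does all the useful work and that the choice of 31 December or 1 July is mere convention. This part fails: with both rules bounded, 31 December still misplaces 8.3% of year-only subjects against about 4% for 1 July, and keeps nearly all of its downward bias.

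**Conclusion.** The point holds as a minor specification defect. The rule biases derived age downward, by 0.5 year on average for year-only dates and about 15 days when only the day is missing. It can also yield an age of 5, which conflicts with inclusion criterion 1 and falls outside every age subgroup. The share of year-only 6-year-olds affected, about half, rests on even timing over the year and ranges from 12% to 86% by quarter of first dose. The 12.5% leaving their band also assumes an even spread of true ages. In completed years, the unit of the age bands, about half of year-only subjects drop a year and about 4% of those with a known month.

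The primary analysis is untouched. The number of children affected cannot be estimated from the documents and may be zero.

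**What to change.** In SAP section 7, impute a missing day as the 15th and a missing day and month as 1 July. Add that, where the site has confirmed inclusion criterion 1, the imputed date is bounded so that age at first dose stays within 6 to <18 years. Both parts are needed: the midpoint removes the bias and halves the band errors, and the bound removes impossible ages at both ends. Tying the bound to the site's confirmation means that it cannot mask a real age deviation.

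The cost is two sentences and a small change to the age derivation. SAP version 2.0 was issued ahead of database release, which is a natural point for such a correction.

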## **8. STATISTICAL METHODOLOGY AND STATISTICAL ANALYSES**

### **8.1. Statistical METHODS**

Treatments will be labeled as follows in all the data summaries:

Cohort 1:

Fesoterodine 4 mg PR

Fesoterodine 8 mg PR

Oxybutynin

Cohort 2:

Fesoterodine 2 mg BIC

Fesoterodine 4 mg BIC

### **8.1.1. Analysis of Continuous Data**

Where data is to be summarized using descriptive statistics the following will be presented: n, mean, standard deviation, median, minimum, and maximum.

### **8.1.2. Analysis of Binary Data**

Binary endpoints will be presented using cell counts and proportions for each response category. For summaries of change from baseline the tables will be presented as a cross tabulation with baseline visit along the side and week 12 results along the top.

## **8.2. Statistical Analyses**

### **8.2.1. Cohort 1: Primary Analysis**

Change from baseline to Week 12 in the primary endpoint will be analysed using an ANCOVA including terms for treatment group, baseline (for the endpoint being analyzed) and baseline weight. The Least Squares mean change from baseline for each treatment group, standard error, 95% confidence intervals and p-values associated with the Least Squares mean changes from baseline will be presented.

All endpoints will also be summarized descriptively for each treatment group, by timepoint as for a continuous endpoint. Should any of the assumptions of the analysis methods not be adequately met, alternative procedures will be used and fully documented.

The following primary comparisons of interest will be assessed:

- Change from Baseline to Week 12 for fesoterodine 4 mg PR.
- Change from Baseline to Week 12 for fesoterodine 8 mg PR.

The Least Squares means and 95% confidence intervals for the difference between each fesoterodine dose group and oxybutynin will also be calculated.

The following secondary comparisons will be assessed using 95% confidence intervals for the difference between treatment means (for the change from baseline to Week 12):

- Fesoterodine 4 mg PR vs Oxybutynin.
- Fesoterodine 8 mg PR vs Oxybutynin.

As these secondary comparisons are based on an estimation approach, no formal statistical hypothesis testing will be performed. Conclusions will be based on point estimates and confidence intervals.

Forest plots presenting the mean and 95% confidence intervals for the change from baseline for Fesoterodine 4mg PR, Fesoterodine 8mg PR and Oxybutynin will be produced. In addition the mean difference and its associated 95% confidence interval between change from baseline for Fesoterodine 4 mg PR vs. Oxybutynin and Fesoterodine 8 mg PR vs. Oxybutynin will be also presented in a separate plot.

The primary analysis will be based on the Full Analysis Set (FAS). The secondary analysis set will be the Per Protocol Analysis Set (PPAS).

Data from the active comparator phase of the study may be summarized, analyzed and reported after all subjects have either completed or withdrawn prior to the Week 12 visit or from both phases after all subjects in Cohort 1 have either completed or withdrawn prior to the end of the study (ie, prior to formal completion of the whole study for both cohorts). If performed, the results of these analyses will be assessed by the EDMC and will be available to limited members of the study team as a management tool in order to aid decision making, and may also be shared with regulators in order to facilitate timely discussion of the overall program; they will not be used to stop or modify the design of the study.

Descriptive subgroup analyses of the change from baseline to Week 12 in the primary endpoint will be produced by age group, weight group, race, ethnicity, gender, region and underlying type of disease.

### **8.2.2. Cohort 2: Primary Analysis**

Change from baseline to Week 12 in the primary endpoint will be analyzed using an ANCOVA including terms for treatment group and baseline (for the endpoint being analyzed). The Least Squares mean change from baseline for each treatment group, standard error and 95% confidence intervals associated with the Least Squares mean changes from baseline will be presented.

All endpoints will also be summarized descriptively for each treatment group, by timepoint, using: N, mean, standard deviation, median, minimum and maximum. Should any of the assumptions of the analysis methods not be adequately met, alternative procedures will be used and fully documented.

The following primary comparisons of interest will be assessed:

- Change from Baseline to Week 12 for fesoterodine 2 mg BIC.
- Change from Baseline to Week 12 for fesoterodine 4 mg BIC.

As these comparisons are based on an estimation approach, no formal statistical hypothesis testing will be performed. Conclusions will be based on point estimates and confidence intervals.

The primary analysis will be based on the Cohort 2 Full Analysis Set (FAS2). The secondary analysis set will be the Cohort 2 Per Protocol Analysis Set (PPAS2).

For the PPAS analysis no imputation techniques for missing data will be employed. For the FAS analysis a Baseline Observation Carried Forward (BOCF) and a Last Observation Carried Forward (LOCF) algorithm will be used for missing data.

Data from the efficacy phase for this cohort may be summarized, analyzed and reported after all patients in this cohort have either completed or withdrawn prior to the Week 12 visit (ie, prior to formal completion of the study). The results of these analyses will be available to limited members of the study team as a management tool in order to aid decision making, and may also be shared with regulators in order to facilitate timely discussion of the overall program; they will not be used to stop or modify the design of the study.

Descriptive subgroup analyses of the change from baseline to Week 12 in the primary endpoint will be produced by age group, weight group, race, ethnicity, gender, region and underlying type of disease.

### **8.2.3. Secondary Analyses**

All secondary endpoints will be analysed as for the primary analyses as defined for each respective cohort using the appropriate full analysis set. A further analysis of the key secondary endpoints of Bladder compliance and IDC will use the per protocol analysis set.

The presence of IDC will be analyzed as for discrete endpoints.

### **8.2.4. Other Endpoints**

The following analyses will be carried out for subjects randomised to Fesoterodine only (for each cohort separately).

#### Pharmacokinetic Concentrations

Plasma concentrations of 5-HMT will be listed and summarized for subjects in the PK analysis set, where missing and BLQ values will be handled as detailed in [Section 7](#).

Presentations will include:

- a listing of all concentrations sorted by visit, dose, subject ID and nominal time postdose. The listing of concentrations will include the actual times.
- if data permit, a summary of concentrations by visit, dose and nominal time postdose, where the set of statistics will include n, mean, median, standard deviation, minimum, maximum, coefficient of variation (cv) and the number of concentrations above the lower limit of quantification.

### Pharmacokinetic Parameters

Model based PK parameters (from POP PK analysis) will be described in a separate plan.

#### **8.2.5. Safety Analyses**

Tables of safety and demographic data, including adverse events and medical history in this report will be reported in accordance with current Pfizer standards, and will be presented separately for each cohort. Safety summaries of both cohorts combined may also be produced. Adverse events will be summarized by treatment group as specified for the Three Tier Adverse Event Reporting and for Other Adverse Event Reporting.

All other safety summaries will be summarised by the following treatment groups (as safety data will be captured throughout the Active Comparator/Efficacy and Safety Extension phases):

Cohort 1:

Oxybutynin -> Fesoterodine 4mg PR

Oxybutynin -> Fesoterodine 8mg PR

Oxybutynin (only)

Fesoterodine 4mg PR -> Fesoterodine 4mg PR

Fesoterodine 8mg PR -> Fesoterodine 8mg PR

Cohort 2:

Fesoterodine 2mg BIC -> Fesoterodine 2mg BIC

Fesoterodine 4mg BIC -> Fesoterodine 4mg BIC

